1 ABBREVIATIONS USED IN THE PROTOCOL

Abbreviation	Term
AE	Adverse event
ASL	Arterial Spin Labelling
CRT	Chemoradiotherapy
EGFR	Epidermal Growth Factor Receptor
EOR	Extent of Resection
GBM	Glioblastoma
GIRB	Geisinger IRB
HGG	High Grade Glioma
IDH	Isocitrate Dehydrogenase
IRB	Institutional Review Board
KPS	Karnofsky Performance Status
MGMT	Methyl Guanine Methyl Transferase
SAE	Serious Adverse Event
TMZ	Temozolamide

2 ABSTRACT

High grade gliomas, particularly glioblastoma, are the most common malignant primary brain tumors in adults(1). Surgical resection, when feasible, offers the best chance of alleviating the mass effect and increasing the likelihood of durable local control. Whether tumors are resected or deemed unresectable, the standard definitive treatment for high grade glioma is involved field radiation with concurrent and adjuvant temozolomide chemotherapy(2). Additional therapy with anti-VEGF therapies(3, 4) and wearable devices such as alternating electric fields(5) have improved progression free and overall survival modestly.

Unfortunately, most patients recur in the region of the primary tumor, ultimately leading to neurological progression and death in a majority of patients(6). One hypothesis for this progression in the region of the primary tumor has been the persistence of resistant clones, including glioma stem cells(7).

Neoadjuvant, preoperative chemo radiation has consistently shown improvements in local disease control or organ preservation in many cancers including head and neck(8), esophageal(9), rectal(10), bladder cancers(11) and sarcomas(12), leading to improvements in overall survival and limb or organ preservation.

Preoperative therapy has not been well studied in resectable glioblastoma. This study attempts to prospectively assess the feasibility and efficacy of preoperative chemoradiation in improving local control, as this is the predominant mode of failure in these patients leading to poor outcomes.

We plan to do this interventional study in two phases using the Simon two-stage Phase II study design(13). Please see section 5.9 on statistical analysis and plan. In the initial stage if there are no more than 3 unanticipated events after 9 patients, an additional 15 patients will be treated in the second stage of this Phase II study. If no more than 9 of the overall 24 patients overall progress in 8 months the study treatment would be considered significant and worthwhile studying in a future randomized phase III study, comparing preoperative study treatment with standard of care post postoperative chemoradiation to evaluate progression free and overall survival as the end point.

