5 STUDY DESIGN

5.1 Description

We plan to do this interventional study in two phases using the Simon two stage Phase II study design(13). Please see section 5.9 – Statistical methods. Given the novel approach of an existing treatment scheme, this two-stage design allows for safety and efficacy evaluation to proceed to the complete phase II study.

If the median progression free survival (PFS) in this study, meets significance at the completion of this study, it would form the basis to continue as a randomized phase III study with PFS as the primary study objective and overall survival as the secondary objective.

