5.2 Study Population

5.2.1 Approximate Number of Subject

Approximately 30 Geisinger subjects will participate in this initial Phase II study.

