5.4 Study Duration

5.4.1 Approximate Duration of Subject Participation

The median progression-free survival for these patients is in the order of 8-12 months, and the median overall survival is in the order of 14-18 months. Subject participation will be from

registration to progression, death or 26 months after the enrollment of the last study participant. This includes registration, study treatment, postoperative phase, adjuvant therapy, and follow-up.

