5.9.1 Statistical Analysis Plan

The Simon two-stage design will be used.

The median progression-free survival of these patients with current standard of care therapy is in the range of 6-8 months (6.9 months in the standard of care). With the proposed trial of surgical resection of the tumor after chemotherapy and radiation the median progression free survival is anticipated to be approximately 11-12 months from subset analysis of available literature and based on prior data on other disease sites. In other words, the 7-month local progression rates is anticipated to decrease from 50% to 25%, or progression free survival improve from 50-75% Due to assessment of unanticipated adverse events with this novel sequencing of established treatment, a Simon two-stage phase II study design would be used to proceed with the study treatment after meeting prespecified events in the initial phase, with goal being to determine whether the new treatment paradigm is sufficiently promising to warrant a major controlled clinical evaluation against the standard therapy

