5.9.2 Statistical Power and Sample Size Considerations

In the Simon two-phase design of this study, if:

p_0 = progression rate of Standard of care = 0.5 (null Hypothesis)

p_1 = Progression after study treatment = 0.25

OR

p_0 = non-progression rate of 0.5

p_1 = non-progression rate of 0.75

With a

Prespecified Type I error rate $\alpha \leq 0.05$

Prespecified Power ≥ 0.8

For non-progression being the response:

The null hypothesis that the true response rate $p_0=50\%$ will be tested against a one-sided alternative. In the first stage $n_1=11$ patients will be accrued. If there are $r_1=6$ or fewer patients responding (i.e. don't progress) in these $n_1=11$ patients, the study will be stopped. Otherwise $n-n_1=14$ additional patients will be accrued to a total of $n=25$. The null hypothesis will be rejected if $r_2+1=17$ or more responses (If >17 of 25 patients do not progress in 7 months) are observed in the ($n=25$) patients. This design yields a type I error rate of 0.05 and a power of 80% when the true response rate (non-progression at 7 months) is $>75\%$.

After completion of 25 patients followed at least for 7 months of the last patient treated, Primary and secondary endpoints will be evaluated and reported.

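### The Abstract and section 5.9.2 state incompatible final success rules, and only the 5.9.2 rule, with its 6-of-11 stop, has stated error rates and meets them

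*Combined protocol and SAP*

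**What the plan says.** **Abstract (section 2).** After a first stage of 9 patients judged on unanticipated events, 15 more are treated. The final rule is: "If no more than 9 of the overall 24 patients overall progress in 8 months the study treatment would be considered significant". The Abstract refers the reader to section 5.9 for the statistics.

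**Section 5.9.2.** The first stage has 11 patients and stops if 6 or fewer do not progress. Otherwise 14 more are accrued, to a total of 25. The null is rejected at 17 "or more responses (If >17 of 25 patients do not progress in 7 months"). The null and alternative non-progression rates are 0.50 and 0.75, the test is one-sided, and the section concludes: "This design yields a type I error rate of 0.05 and a power of 80" per cent.

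**Section 5.9.1.** This also works at 7 months: "the 7-month local progression rates is anticipated to decrease from 50% to 25" per cent. It puts median PFS on current standard care "in the range of 6-8 months (6.9 months in the standard of care").

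**First stage and totals elsewhere.** Section 5.7 describes stage 1 by undue toxicity or progression and gives no patient number. Section 7.3 has 10 patients and discontinues at 3 or more unexpected toxicities. Section 5.2.1 says: "Approximately 30 Geisinger subjects will participate in this initial Phase II study".

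**Section 5.1.** The move to phase III is tied to a different quantity: "If the median progression free survival (PFS) in this study, meets significance at the completion of this study".

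**The concern.** The final rule decides whether a phase III trial is recommended. A protocol with two such rules leaves open which one applies, and in a single-arm trial of about 25 patients the choice could be made after the outcomes are known.

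The conflict cannot be removed by rewording one number. Three elements differ (24 or 25 patients, 8 or 7 months, 15 or 17 progression-free), and so does the first stage that comes before the final test. The error rates in 5.9.2 belong to one specific two-stage design. If the trial applies another document's first stage and then the 5.9.2 final cut-off, those error rates no longer describe the trial.

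**Working it through.** **Inputs.** From 5.9.2: p0 = 0.50, p1 = 0.75, n1 = 11, stop at 6 or fewer, n = 25, reject at 17 or more. From the Abstract: 24 patients and at most 9 progressions, so 24 − 9 = 15 or more progression-free at 8 months.

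**Formula.** For a two-stage rule, P(reject) = Σ P(X1 = x) · P(X2 ≥ r − x), summed over first-stage counts x above the stopping limit. X1 and X2 are binomial, and r is the final cut-off.

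**Step 1: reproduce 5.9.2.** X1 ~ Bin(11, p), X2 ~ Bin(14, p), r = 17.

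| x | needed of 14 | product at p = 0.50 | product at p = 0.75 |
|---|---|---|---|
| 7 | 10 | 0.16113 × 0.08978 = 0.01447 | 0.17207 × 0.74153 = 0.12760 |
| 8 | 9 | 0.08057 × 0.21198 = 0.01708 | 0.25810 × 0.88833 = 0.22928 |
| 9 | 8 | 0.02686 × 0.39526 = 0.01061 | 0.25810 × 0.96173 = 0.24823 |
| 10 | 7 | 0.00537 × 0.60474 = 0.00325 | 0.15486 × 0.98969 = 0.15327 |
| 11 | 6 | 0.00049 × 0.78802 = 0.00038 | 0.04224 × 0.99785 = 0.04214 |
| Sum | | **0.0458** | **0.8005** |

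The stated alpha and power are reproduced. A search over two-stage designs meeting both targets shows that this one has the smallest expected sample size under the null (14.84). It is therefore the Simon optimal design for these inputs.

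**Step 2: what the 5.9.2 figures depend on.**
- Without the 6-of-11 stop, P(X ≥ 17 | 25) is 0.0539 at 0.50 and 0.8506 at 0.75. Alpha exceeds the 0.05 limit.
- With the stop but the parenthesis read literally (18 or more of 25), the values are 0.0200 and 0.7011. Power falls short of 80%.

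**Step 3: the Abstract rule at the plan's only stated rates.** With no progression stop, P(X ≥ 15 | 24) is 0.1537 at 0.50 and 0.9453 at 0.75. If its limit of 3 events in 9 patients is read as a limit on progressions, which the Abstract does not say, the values are 0.0989 and 0.8148.

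**Step 4: sensitivity to the time point.** The plan gives no 8-month rates. Assuming constant hazard, the 7-month rates become 0.50^(8/7) = 0.453 and 0.75^(8/7) = 0.720. The Abstract rule then gives 0.068 and 0.894 with no progression stop, or 0.043 and 0.737 with the 3-of-9 reading. Alpha for the null medians in 5.9.1, on the same assumption:

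| null median (months) | Abstract, no stop | Abstract, 3-of-9 reading | 5.9.2 |
|---|---|---|---|
| 6 | 0.020 | 0.012 | 0.013 |
| 6.9 | 0.062 | 0.038 | 0.041 |
| 8 | 0.154 | 0.099 | 0.107 |

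**Step 5: the same data, two verdicts.** Suppose 5.9.2's first stage is passed.
- 16 of the first 24 patients are progression-free at both 7 and 8 months, and patient 25 progresses early. The Abstract rule is met (16 ≥ 15) and 5.9.2 is not (16 < 17).
- 17 of 25 are progression-free at 7 months, patient 25 is among the 8 who progressed, and 3 more progress before month 8. Section 5.9.2 is met, and the Abstract rule is not (17 − 3 = 14 of 24).

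**The case against.** The strongest reply is that the Abstract is a summary and sends the reader to 5.9, which is complete and arithmetically correct. On that view the Abstract is merely out of date. This stands as a reason for keeping 5.9.2. It does not remove the conflict: the Abstract's rule is current text, complete in itself, and names the phase III consequence.

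A reader might infer that the Abstract sets the lower bar, since 15/24 = 62.5% and 16/24 = 66.7% are below 17/25 = 68%. The documents do not support this, because the first two are 8-month proportions and the third is a 7-month proportion. Under constant hazard, 62.5% at 8 months corresponds to 0.625^(7/8) = 66.3% at 7 months, and 66.7% corresponds to (16/24)^(7/8) = 70.1%, which is above 68%. The null-median table shows the same: with the 6.9-month standard-of-care median, the Abstract's alpha is 0.062 or 0.038 depending on how its first stage is read, against 0.041 for 5.9.2.

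Nor can it be said that the Abstract rule must fail the plan's targets. With a 6-month null median, no progression stop and an 8-month alternative of 0.720, it would have alpha 0.020 and power 0.894. The 0.154 applies the plan's 7-month null at 8 months, and is shown because the plan states no other.

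**Conclusion.** The point holds as an inconsistency in the decision rule, and it should be corrected before outcomes are evaluated. The two rules differ in sample size, time point and cut-off, and can give opposite conclusions in either direction. No general claim is made about which is stricter.

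Of the two rules, only 5.9.2 has stated hypotheses and error rates, and it delivers them: exact alpha 0.046 and power 0.80. This requires that the 6-of-11 non-progression stop is applied and that the cut-off is 17. These results are exact binomial at the plan's own rates and need no survival assumption. The 8-month figures and those based on medians do assume constant hazard.

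The first-stage conflict matters here because the 5.9.2 alpha depends on that stage. The Abstract, 5.7, 5.9.2 and 7.3 give different patient numbers or different events. With exactly three events, the Abstract continues while 7.3 discontinues. The median-PFS wording in 5.1 is minor.

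**What to change.** 1. In the Abstract, replace the final rule with the 5.9.2 rule in its own form: 17 or more of 25 patients progression-free at 7 months. This is safer than a limit of 8 progressions, because the two are equivalent only if all 25 patients are evaluable at 7 months.
2. In the 5.9.2 parenthesis, change more than 17 of 25 to 17 or more of 25.
3. In the same amendment, the sponsor should reconcile the first-stage statements: Abstract (9 patients, unanticipated events), 5.7 (toxicity or progression, no number), 5.9.2 (11 patients, non-progression) and 7.3 (10 patients, toxicities). The total should be reconciled too (24, 25 or about 30), with the Abstract's 9 + 15 split. This review does not choose the toxicity stopping rule.
4. If the 6-of-11 progression stop is changed or dropped, recompute and restate alpha and power.
5. Minor: in 5.1, refer to the 5.9.2 rule instead of a significant median PFS.

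Items 1, 2 and 5 are wording and add no patients to the 25 in 5.9.2. Item 3 needs a sponsor decision. Item 1 should not be issued without it, or a 9 + 15 accrual would stand beside a rule for 25.

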3 BACKGROUND AND SIGNIFICANCE

Malignant gliomas are the most common primary central nervous system tumor in adults, and glioblastoma multiforme (GBM) represents the most aggressive and prevalent subtype of these tumors(6). Approximately 12,000 cases of GBM are diagnosed in the United States each year, and the incidence of GBM has been increasing over the past decade, with the peak occurrence after the age of 40(1, 14).

Despite surgery, conventional radiotherapy, and chemotherapy, the median survival for GBM remains poor at approximately 15-16 months in contemporary series(15). Although adjuvant chemoradiotherapy has been shown to increase survival, the predominant pattern of failure remains local(16).

3.1 Surgery

Surgical resection of GBMs after diagnosis is used to relieve mass effect, confirm the diagnosis pathologically, and set the stage for multimodal adjunctive therapy(17). Lacroix et al. reported on the outcomes of 416 patients with newly diagnosed and recurrent GBMs(18). The authors found that an extent of resection of 98% or more was associated with improved survival. More recently, Marko et al. reported the outcomes of 500 newly diagnosed GBM patients undergoing initial resection(19). With modern surgery, significant survival benefits were observed with resection of as little as 78% but increased as the extent of resection approached 100%, at which point median overall survival exceeded 16 months (compared with 12.2 months for the entire cohort).

3.2 Adjuvant Chemoradiation

After surgical resection of all or part of the tumor, radiation therapy with concurrent and adjuvant temozolomide remains the most effective single standard adjuvant treatment for newly diagnosed GBMs(2).

Chemoradiation is often employed to treat unresectable or sub totally resected GBM. Radiating native GBM is not uncommon as many tumors are not safely resectable due to its location in eloquent brain. Also, surgical resection is often performed in patients who recur after initial definitive treatment with chemo radiation. Hence, this approach of

chemoradiation of native glioblastomas and surgical resection after prior chemoradiation is not entirely new. However, planned neoadjuvant chemoradiation prior to immediate surgical resection in glioblastoma is the novel approach.

3.3 Local Failure

Although radiation therapy prolongs median survival, most patients eventually experience infield recurrences that ultimately lead to death. Increasing doses of conventional radiation therapy beyond the standard of 60 Gy is limited by potential toxicity to the normal brain and has not resulted in improved survival(20). Furthermore, complications of radiation correlate directly with the overall target volume treated. In all disease sites comparing preoperative versus postoperative adjuvant radiation, preoperative treatment volumes are consistently smaller. Considering that 90% of recurrences in malignant gliomas are located within 2 cm of the enhancing edge of the original tumor on scans and that the occurrence of multicentric disease or metastatic spread is rare(21), treatments that increase the dose or dose effectiveness to a localized tumor without increasing radiation to the adjacent normal brain tissue are attractive approaches that may improve the therapeutic ratio. However, no significant impact has been made over the last few decades on improvements in local control and survival beyond standard adjuvant chemoradiation. In other disease sites with resectable local disease, where local recurrence is a significant problem, neoadjuvant therapy has consistently shown improvement in local control of up to 50%.

3.4 Neoadjuvant Therapy

Delivering CRT in the neoadjuvant setting has the promise to remedy the pitfalls associated with adjuvant CRT approaches that results in delays and poor compliance. Postoperative complications may limit compliance with adjuvant CRT. Earlier delivery of full-dose CRT therapy to eliminate marginal micro metastatic disease has the potential to decrease the risk of disease progression and improve disease-related outcomes(22). Improved local control and decreased toxicity has been consistently demonstrated with preoperative CRT in esophagogastric(23), pancreatic(24), rectal(25), bladder(26) and soft tissue sarcomas(27) and thereby leading in many instances with improved survival (esophageal and rectal cancer) and organ preservation (larynx and bladder cancer).

3.5 Stem cell hypothesis in Glioblastomas

A promising new approach to treat glioblastoma proposes targeting cancer stem cells. The cancer stem cell hypothesis proposes that cancers derive from a small fraction of cancer cells that constitute a reservoir of self-sustaining cells with the exclusive ability to divide asymmetrically to self-renew and maintain the tumor. These stem-cell-like cancer cells make up just a small fraction of the malignant cells in many solid tumors, but they are solely responsible for propagating the disease in laboratory models. They were first isolated from glioblastomas by the expression of CD133 that marks neural stem and progenitor cells. The existence of glioblastoma stem cells (GSCs) and the discovery of vascular stem cell niches in the normal brain suggest a further sinister role for the tumor vascular bed: the formation of abnormal stem cell niches that maintain the cancer stem cells(28). As well as regulating stem cell proliferation and cell-fate decisions, niches also have a protective role, shielding stem cells from environmental insults. Thus, GSCs are inherently radio-resistant and might be protected further from conventional therapies by factors within the vascular niche, enabling these cells to reform a tumor mass following an initial clinical response(29). Due to intrinsic resistance, there is a suggestion that GSCs are preferentially enriched after traditional chemo radiation. Also, there is emerging data of upregulation of CD133 cell population after standard chemo radiation(30). Treatments aimed to disrupt and remove stem cell niches after standard therapy with surgical resection could prove to be beneficial in glioblastoma outcomes.

4 HYPOTHESIS AND SPECIFIC AIMS

4.1 Hypothesis

After standard treatment of GBM with resection and adjuvant therapy, local failure is the dominant pattern of failure. Neoadjuvant therapy consistently provides the potential for improved local control and removal of residual stem cell niches. The hypothesis is that earlier institution of neoadjuvant chemoradiation therapy in GBM would improve local control and potentially overall survival.

Involved field radiation is often employed to treat unresectable or sub totally resected GBM. Radiating native GBM is not uncommon as many tumors are not safely resectable due to its location in eloquent brain. Also, surgical resection is often performed in patients who recur

after initial definitive treatment with chemo radiation. Hence, this approach of chemoradiation of native glioblastomas and surgical resection after prior chemoradiation is not entirely new. However, planned neoadjuvant chemoradiation prior to immediate surgical resection in glioblastoma is a novel approach.

4.2 Specific Aim 1

Feasibility of neoadjuvant therapy in GBM to improve local control (local progression free survival) without significant impact of preoperative chemotherapy and radiation on surgical resection.

4.3 Specific Aim 2

To determine the progression free survival with this approach.

Assess the impact of improvements in local control on overall survival.

5 STUDY DESIGN

5.1 Description

We plan to do this interventional study in two phases using the Simon two stage Phase II study design(13). Please see section 5.9 – Statistical methods. Given the novel approach of an existing treatment scheme, this two-stage design allows for safety and efficacy evaluation to proceed to the complete phase II study.

If the median progression free survival (PFS) in this study, meets significance at the completion of this study, it would form the basis to continue as a randomized phase III study with PFS as the primary study objective and overall survival as the secondary objective.

5.2 Study Population

5.2.1 Approximate Number of Subject

Approximately 30 Geisinger subjects will participate in this initial Phase II study.

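### The plan gives three sample sizes (about 30, 25 and 24), but its stated error rates belong to one rule on exactly 25 patients, and it does not say which 25 of about 30 participants count or whether any may be replaced.

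*Combined protocol and SAP*

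**What the plan says.** Three current sections of the combined protocol and SAP give different totals for the same trial.

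- Section 5.2.1: "Approximately 30 Geisinger subjects will participate in this initial Phase II study".
- Section 5.9.2: "In the first stage $n_1=11$ patients will be accrued". The trial stops if 6 or fewer of the 11 are progression-free; otherwise 14 more are accrued, for a total of 25. The null is rejected at 17 or more non-progressors of 25 at 7 months. The analysis is timed thus: "After completion of 25 patients followed at least for 7 months of the last patient treated".
- Section 2 (Abstract): 9 patients, then 15 more, with success defined as follows: "If no more than 9 of the overall 24 patients overall progress in 8 months".

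The design targets are in 5.9.2: "The null hypothesis that the true response rate $p_0=50\%$ will be tested against a one-sided alternative"; "p_1 = non-progression rate of 0.75"; a type I error of at most 0.05; and "Prespecified Power ≥ 0.8". Section 5.7 assigns the stage 2 endpoint to the entire cohort without defining that cohort further. No section explains the roughly five participants above 25, defines an evaluable set, gives a replacement rule, or says how to count a patient whose 7-month status is unknown.

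**The concern.** The trial's conclusion is a count compared with a fixed bound, and that conclusion decides whether a randomised phase III trial follows (sections 2 and 5.1). Such a rule has known error rates only if the denominator and its members are fixed before outcomes are seen. With about 30 participants and a rule for 25, someone must later choose which patients count. This is a single-arm trial, so no control group would expose a favourable choice.

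Early loss is foreseeable. Chemoradiation takes weeks 1-7 and surgery falls in weeks 8-12 (section 5.6), and section 5.7 itself anticipates progression that prevents surgery and failure to complete neoadjuvant therapy. Patients lost in these ways are more likely than others to be failures at 7 months. If they were set aside and their places refilled, the counted 25 would be enriched for responders.

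**Working it through.** **Inputs (section 5.9.2).** p0 = 0.50, p1 = 0.75; stage 1 n1 = 11, continue if 7 or more respond; total n = 25, reject at 17 or more. The same sentence also writes the bound as more than 17. The check uses 17 or more, because that reading reproduces the stated power; 18 or more gives alpha 0.020 and power 0.70.

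**1. The plan's own figures.**

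P(reject | p) = sum over x = 7 to 11 of P[Bin(11, p) = x] × P[Bin(14, p) ≥ 17 − x].

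| x | p = 0.50 | product | p = 0.75 | product |
|---|---|---|---|---|
| 7 | 0.16113 × 0.08978 | 0.01447 | 0.17207 × 0.74153 | 0.12760 |
| 8 | 0.08057 × 0.21198 | 0.01708 | 0.25810 × 0.88833 | 0.22928 |
| 9 | 0.02686 × 0.39526 | 0.01061 | 0.25810 × 0.96173 | 0.24823 |
| 10 | 0.00537 × 0.60474 | 0.00325 | 0.15486 × 0.98969 | 0.15327 |
| 11 | 0.00049 × 0.78802 | 0.00038 | 0.04224 × 0.99785 | 0.04214 |
| Sum | | **0.0458** | | **0.8005** |

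The stated 0.05 and 80% are right for this rule. A search of two-stage designs up to n = 30 returns the same one as Simon's optimal design.

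**2. Thirty counted, stage 1 unchanged.** Replace 14 by 30 − 11 = 19 in the formula.

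- Bound left at 17: alpha 0.162, power 0.883.
- Bound raised to 20: alpha 0.040, power 0.826.

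**3. Replacement of failures (assumed, not in the plan).** Let d failures be removed and their places refilled, so that 25 of 25 + d enrolled are counted, under p0 = 0.50. The stage 1 and final bounds stay at 6/11 and 17/25. The random column is exact: sum over s = 17 to 25 of P[Bin(25 + d, 0.5) = s] × P[at least 7 of the first 11 respond, given s responders among the 25 kept].

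| d | all removed in stage 2 | removed at random | first d failures removed |
|---|---|---|---|
| 1 | 0.066 | 0.072 | 0.08 |
| 2 | 0.090 | 0.107 | 0.12 |
| 3 | 0.114 | 0.151 | 0.17 |
| 4 | 0.139 | 0.202 | 0.22 |
| 5 | 0.162 | 0.260 | 0.29 |

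A simpler approximation raises the null rate among counted patients to 0.5 × (25 + d)/25, that is 0.52 to 0.60. It gives 0.068, 0.098, 0.136, 0.183 and 0.240 for d = 1 to 5, inside the same range. If removal does not depend on outcome, the counted rate stays at 0.50 and alpha stays at 0.046.

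**4. Cost of counting unknown status as progressed.** With a fraction L unevaluable, independent of outcome, the effective response rate under the alternative is 0.75 × (1 − L).

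| L (assumed) | effective rate | power, 17/25 | power, 20/30 |
|---|---|---|---|
| 0 | 0.750 | 0.80 | 0.83 |
| 4% | 0.720 | 0.70 | 0.73 |
| 5% | 0.7125 | 0.67 | 0.70 |
| 10% | 0.675 | 0.52 | 0.54 |

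**The case against.** A reader might infer that nothing fixes who is counted and that the plan therefore runs at a false-positive rate of 16% to 24%. The documents do not support that.

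- Section 5.9.2 caps accrual at 25 and ties the bound to those 25, and section 5.7 speaks of the entire cohort. Read together, the natural meaning is that every accrued patient counts, up to 25. Section 5.2.1 offers an approximate headcount, not a decision rule.
- No section mentions replacement. In the sentence of 5.9.2 that times the analysis, the reference to treatment describes the last patient; it does not define a treated-only set.
- Section 5.7 lists progression that prevents surgery and non-completion of neoadjuvant therapy (apart from protocol-defined dose adjustments or discontinuation) as stage 1 events. That points towards counting such patients, not discarding them.
- The surplus could be consented patients who fail screening: consent and biopsy both fall in the screening column of section 5.6, and registration follows confirmed eligibility (5.5.1). That would leave alpha untouched.
- The 16% needs a bound of 17 kept for 30 patients, which nobody proposes. The 24% needs all five extra places to have been used to remove failures.

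Most of this stands, and it limits the point to an unresolved contradiction. It does not remove it. The documents do not give the screening explanation, and 5.2.1 counts people who will participate. If about 30 do participate, the entire cohort is about 30, for which there is no bound. The stage 1 event list concerns toxicity and feasibility; it does not say who enters the 7-month count.

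**Conclusion.** The point holds in limited form. The totals of about 30, 25 and 24 conflict in current text, and the stated operating characteristics (exact alpha 0.046, power 0.80) belong only to the 6/11, 17/25 rule. What is missing is which 25 of about 30 participants count, whether replacement is allowed, and how unknown 7-month status is handled.

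The inflated error rates are scenarios, not properties of the written plan. Alpha is 0.16 if 17 is applied to 30 patients, and about 0.07 (one failure replaced) to 0.29 (the first five replaced) under outcome-dependent replacement. The reproduced baseline is firm; the number and timing of any replacements are assumptions, because the documents give neither. The contradiction should be corrected before analysis, since the go/no-go conclusion rests on this count.

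**What to change.** 1. State one total and one decision rule in sections 2, 5.2.1 and 5.9.2, with the final bound written one way only.
2. Define the decision set as the first 25 registered patients, with no replacement of patients who progress, miss surgery or stop early. Describe any enrolment above 25 as outside the decision rule.
3. If 30 are to be counted instead, keep 6/11 at stage 1 and require 20 or more of 30 (alpha 0.040, power 0.83).
4. State in advance how a missing 7-month status is counted.

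Items 1 and 2 cost only wording. Item 3 commits the trial to five more counted patients than the present rule. Item 4 can be expensive, because power of 0.8005 leaves no slack. If missing status is counted as progressed, power for 17/25 falls to about 0.67 with 5% unevaluable and 0.52 with 10% (assumed rates, independent of outcome). The 20-of-30 rule gives little protection, at 0.70 and 0.54. The plan should disclose this loss and aim to keep missing 7-month assessments to a minimum. It is not a reason to leave the choice until outcomes are known.
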